- 5) To explore the effects of an early literacy promotion program compared to standard literacy promotion on social-emotional development among poor urban children in Philadelphia.

Study Design:

A randomized controlled trial will be conducted comparing two versions of the parent-child reading program: Early literacy promotion (ELP) and Standard Literacy promotion (SLP). An additional sub-study will utilize semi-structured interviews with a purposive number of parents enrolled in the study to explore barriers and promoters to reading to their children.

Setting/Participants:

We will recruit participants who are English or Spanish speakers, at least 15 years old, the parent of a child born ≥ 35 weeks gestation age and < 4 weeks at enrollment and with Medicaid insurance. We will be recruiting from one urban site affiliated with CHOP (Karabots). The combined total enrollment number of participants will be 240 (120 dyads of parent and infant). The target enrollment number of participants for the sub-study will be up to 30 parents.

Study Interventions and Measures:

In this intervention, parents/children randomized to the ELP arm will receive a book with developmentally appropriate advice about reading at each well child visit from one week through 5 months of age, as well as weekly text reminders related to reading. Those in the SLP arm will receive weekly text messages about child safety. From 6 months of age, both groups will receive SLP and will attend study visits every six months until age 2. Difference between the groups on the PLS (Pre-school language score-5th edition) score at 6 and 24 months of age are the main outcomes. StimQ score differences at 6,12,18, and 24 months of age will be a secondary outcome. Other outcomes include score differences at 12, 18, and 24 months in the PHQ-9 and the PSI-Short Form, and differences in the ITSEA at 18 and 24 months. A purposive sample of parents will participate in a qualitative interview component to understand barriers to reading, parents' perceptions of the value of reading to infants, and factors which promote reading.

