2.2 Secondary Objectives

Specific Aim 2: To explore whether Parent history of adversity, health literacy, parenting stress, and depression moderate the effects of early literacy promotion.

Specific Aim 3: To explore whether the effects of early literacy promotion are mediated through the intensity of reading behaviors.

Specific Aim 4: To identify perceptions of barriers to and promoters of reading behavior among parents with high and low ACE scores.

Specific Aim 5: To explore the effects of an early literacy promotion program compared to standard literacy promotion on social-emotional development among poor urban children in Philadelphia.

Specific Aim 6: To explore the impact of early literacy on healthcare utilization

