Children randomized to the standard literacy promotion arm will receive developmentally appropriate books and information on the importance of parent-child reading activity by pediatric clinicians beginning with the 6-month well child visit and weekly text message reminders concerning child safety. This conforms to the ROR National Program recommendations and is considered standard of care at these 3 urban clinics. To prevent contamination in which pediatric clinicians inadvertently provide books and instruction on reading activity to control children prior to 6 months of age, a research assistant will ensure that books and reading instruction are not provided to children in this arm prior to 6 months of age. The weekly text message reminders will be initiated following enrollment, will be standardized according to age, and will be scheduled according to parent preference in the morning, afternoon, or evening.

Children in both study arms will be followed every 6 months until age 2. Information on reading activities, expressive and receptive language outcomes, parental mental health, and child's social and emotional competencies will be collected in concert with scheduled well child visits. Differences in reading activities, parental mental health, child's social/emotional competencies, and language outcomes will be assessed between groups using intention-to-treat analysis.

A purposive sample of up to 30 parents of infant less than 6 months old who have consented to participate in the main study will additionally be recruited to participate in semi-structured interviews with aims to have an equal mixture of parents with high and low exposure to adversity. High adversity is defined for the purpose of this study as having an ACE score of 2 or greater. Low adversity is defined for the purpose of this study as having an ACE score less than 2. Parents with infants less than six months of age are specifically being targeted for the interviews to understand factors that affect this specific age group. The interviews will aim to explore and to understand barriers to reading, parents' perceptions of the value of reading to infants, and factors which promote reading in this population

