3.1.1 Screening Phase

Children who attend these clinics are primarily poor (72% Medicaid) and diverse racially with 80% being African-American, 10% white, 5% Hispanic, and 5% Asian. Children will be eligible to participate in this study if they were born ≥ 35 weeks estimated gestational age, without neurodevelopmental disabilities or congenital malformations, with Medicaid insurance (proxy measure for poverty), and < 30 days old at the time of enrollment. Children who are born premature < 35 weeks EGA, who have neurodevelopmental disabilities, or who have congenital malformations are at increased risk of language delays and will be excluded. In addition, we will exclude families who do not speak English or Spanish, as the main measures of reading activity (StimQ, Appendix 6) and language development (Preschool Language Scale-V, Appendix 7) are only available in English and Spanish.

Potential subjects will be identified at the time of their first well child visit < 30 days of life using the electronic health record (EHR). Eligible newborns' parents will be approached at the time of their child's appointment by research staff. They will obtain written informed consent from participants in private. Participants will be randomized to receive either the early literacy promotion arm or the standard literacy promotion arm based on random assignment.

Randomization sequences will be developed by the project biostatistician using computer-generated random numbers prior to study enrollment and will be placed in sealed opaque envelopes. Randomization will ensure equivalence between groups on measured and unmeasured characteristics and is considered to be the strongest protection against bias in study design. Written informed consent will be obtained prior to any study related procedures being performed in person. Consent will include a discussion of study rationale, procedures, measures, benefits, risks, and alternatives to participation. After consent, subjects will either be assigned to the literacy promotion arm or the standard literacy promotion arm of the study. Regardless of their assignment, once they have consented to participate, they will complete a demographic questionnaire (Appendix 1), questionnaires about adverse childhood experiences (Appendix 2), and health literacy (Appendix 3) and the Edinburgh Postnatal Depression Scale (EPDS) (Appendix 4) prior to the intervention.

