 - Parents will complete measures of reading activity (Stim-Q) at each study visit.
 - Children will complete measure of child expressive and receptive language development (Preschool Language Scale-V) at 6- and 24-month visits.
 - At the 12-, 18-, and 24-month visits, parents will complete the PSI and PHQ-9 questionnaires.
 - At the 18- and 24-month visits, parents will also complete the ITSEA about their child.

4) STUDY EVALUATIONS AND MEASUREMENTS

a. Screening and Monitoring Evaluations and Measurements

i. Parent Adversity (ACE)

The 9 ACE questions query adults as to their exposure to 9 different adverse childhood experiences (economic hardship, domestic violence, parent mental health, discrimination, parent substance abuse, divorce, parent death, parent incarceration, and neighborhood violence) and are contained in the 2011-12 National Survey of Children's Health, a nationally representative telephone survey.

ii. Parent Health Literacy (SAHL)

The Short Assessment of Health Literacy (SAHL) is a validated measure of health literacy for English- and Spanish-speaking populations.

iii. Parent Depressive Symptoms (EPDS)

The Edinburgh Postnatal Depression Scale (EPDS) is a validated 10-item scale for postpartum depression symptoms with scores ≥ 9 having a sensitivity of 97% and specificity of 43% for major or minor depression.

iv. Reading Activity (StimQ)

The StimQ is an office measure of cognitive stimulation at home available in Spanish and English, and the Read subscale of the StimQ contains questions on the frequency of parent-child reading activity and the number and variety of books at home.²⁴ Psychometric analysis of the StimQ shows high internal consistency (Cronbach's Alpha=0.89) and test-retest reliability ($r=0.84$) and moderate correlation with the Bayley Scales of Infant Development ($r=0.52$, $p<0.001$).

We will also use a brief reading questionnaire (Appendix 12) about when participants began reading to their child and what influenced that decision.

v. Language Development (PLS)

The Preschool Language Scale-5th Edition (PLS) is a validated measure of expressive and receptive language function among children from birth through 7 years of age and is available in Spanish and English. The PLS has been standardized in over 1400 children nationally with a sensitivity of 0.83 and a specificity of 0.80 for the detection of language delay.

vi. Infant Toddler Social Emotional Assessment (ITSEA)

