The primary endpoint will be differences in PLS scores at 6 and 24 months of age.

b. Secondary Endpoints

Secondary endpoints will be the difference in StimQ scores at 6, 12, 18, and 24 months of age and the ITSEA scores at 18 and 24 months of age.

c. Statistical Methods

Summary statistics will be obtained, and differences between intervention and control groups will be assessed using intention-to-treat analysis. Cross-sectional differences in StimQ scores and PLS scores between intervention and control groups at the 6 and 24 month study visits and differences in ITSEA scores at 18 and 24 month study visits will be assessed using t-tests. To determine whether early literacy promotion is associated with greater language development, we will develop regression models using longitudinal data methods that adjust for correlation in PLS scores over time and for potential confounding by demographic characteristics. To explore whether early literacy promotion is associated with greater child socio-emotional development, we will develop regression models for scores at 18 and 24 months that adjust for potential confounding by demographic characteristics. To explore the impact of early literacy on healthcare utilization, the EHR will be reviewed to identify a subjects number of well visits and their vaccination history.

To determine whether parent adversity, health literacy, parenting stress, and/or depression modify the effects of early literacy promotion on language development, we will develop similar regression models using longitudinal data methods, but we will also fit interaction terms between study group and ACE score (≥ 4), SAHL (high or low), PSI score, and EPDS score (> 9) or PHQ-9 Score (> 4). To determine if parent-child reading activity mediates the association of intervention group assignment and language development, we will use mediation analysis with separate models regressing group assignment on language development, parent-child reading activity on group assignment, and group assignment on language development adjusted for parent-child reading activity.

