8.6.2 Gifts

Parents participating in the intervention will receive tote bags at their enrollment and four books over the course of the first four months of the study, one at each well visit (enrollment within first week of life, 1 month, 2 month, and 4 months). All parents will receive a small gift to thank them for participating at the end of the final study visit.

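### StimQ asks about books at home and only the ELP arm is given books before 6 months, so a StimQ difference cannot by itself be read as more reading

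*Combined protocol and SAP*

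**What the plan says.** - **What the score contains.** Section 4)a.iv describes StimQ as an office measure of cognitive stimulation at home and adds that "the Read subscale of the StimQ contains questions on the frequency of parent-child reading activity and the number and variety of books at home".
- **Its role.** Section 5)b: "Secondary endpoints will be the difference in StimQ scores at 6, 12, 18, and 24 months of age". Section 5)c plans t-tests on StimQ at 6 and 24 months. The follow-up procedures in section 3)c label it as reading activity: "Parents will complete measures of reading activity (Stim-Q) at each study visit". Section 3.1.1 gives it the same label.
- **What the ELP arm is given.** Section 8.6.2: "four books over the course of the first four months of the study, one at each well visit", that is at enrollment, 1, 2 and 4 months. Sections 3.1 and 3)b give the same four visits.
- **What controls are given.** Sections 3.1 and 3.1.2: "a research assistant will ensure that books and reading instruction are not provided to children in this arm prior to 6 months of age".
- **After that.** The Abstract: "From 6 months of age, both groups will receive SLP".
- **Mediation.** Aim 3 (section 2.2) asks whether effects are "mediated through the intensity of reading behaviors". Section 5)c uses parent-child reading activity as the mediator and names no score for it.

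**The concern.** One arm is handed part of what the outcome asks about, and research staff keep the clinic from giving the same thing to the other arm until 6 months. The StimQ comparison can thus record delivery of the intervention alongside any change in what parents do. Randomization and intention-to-treat analysis do not remove this, because the book supply follows from assignment itself.

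Two conclusions are at stake. The first is any statement that early promotion led parents to read more. The second is Aim 3, which section 9 earmarks for its own manuscript: a mediator that includes supplied books would credit book supply to reading intensity.

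**Working it through.** **Step 1: books supplied against items asked.** Before the 6-month assessment the study supplies 4 books to each ELP family that attends all four visits (section 8.6.2) and 0 to controls (sections 3.1 and 3.1.2). The planned contrast is 4 − 0 = 4 books. The Read subscale asks about number and variety of books (section 4)a.iv). Study visits coincide with well visits (section 3)c), and the order of the StimQ interview and the control arm's first book at 6 months is not stated. From 6 months both arms follow the same programme, so the contrast is sharpest at 6 months. Nothing in the text shows whether it persists to 12, 18 or 24 months.

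**Step 2: does the plan separate the two parts?** No. Sections 5)b and 5)c do not split frequency items from book items, exclude study-supplied books, say whether total StimQ or Read is used, or plan a sensitivity analysis. The other reading instrument, the brief questionnaire in Appendix 12, is described as covering when reading began and what prompted it, so on that description it does not supply a frequency measure.

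**Step 3: the plan's own figure.** The plan gives no StimQ effect size or SD. Its one computed figure is the PLS sample size of 120 (60 per arm) in section 5)c. No SD is stated there either. With 20% loss, 60 × 0.8 = 48 per arm remain, and the implied SD is 4 / [(1.960 + 1.282) × √(2/48)] = 6.05 points; an SD of 6 returns 48 evaluable and 60 recruited per arm. That figure can be back-solved but not verified, and this point does not depend on it. Only the numbers per arm are carried forward.

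**Step 4: illustration.** Suppose reading is unchanged and the book items alone move the mean score by d SD. The chance of a two-sided 5% result is approximately

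Φ(d/√(2/n) − 1.960) + Φ(−d/√(2/n) − 1.960).

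For d = 0.2 and n = 48: √(2/48) = 0.204, d/0.204 = 0.980, and Φ(−0.980) + Φ(−2.940) = 0.165.

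| Assumed shift (SD) | n = 48, normal | n = 48, noncentral t | n = 60, normal |
|---|---|---|---|
| 0 | 5.0% | 5.0% | 5.0% |
| 0.1 | 7.8% | 7.7% | 8.5% |
| 0.2 | 16.5% | 16.3% | 19.5% |
| 0.3 | 31.2% | 30.7% | 37.6% |
| 0.4 | 50.0% | 49.2% | 59.1% |
| 0.5 | 68.8% | 67.9% | 78.2% |

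The 48 reflects loss over the full two years. At 6 months less loss would be expected, so the number would lie between the two columns if the plan's loss assumption holds. The shifts themselves are assumptions; the documents support no particular value.

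**Step 5: mediation.** Write the effect of assignment on the StimQ mediator as a = a_f + a_b, for the frequency and book parts, and let b be the association of the mediator with PLS adjusted for assignment. The product-form indirect effect is a × b. If reading does not change, a_f = 0 and the product is a_b × b. It is non-zero whenever a_b and b are, and it would be reported as mediation through reading.

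**The case against.** The case against has several parts, and most of them limit the point without removing it.

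- **Scoring is unseen.** The text says only what the subscale asks about. The instrument is in Appendix 6, which is not reproduced. If book items are banded, capped or lightly weighted, four books may move the score little or not at all. If the total score is analysed, the book items are a smaller share still. This stands: a reader might infer that the ELP score must rise, but the documents support only that it can.
- **More books is a real gain.** StimQ is described as a measure of cognitive stimulation at home, and books are part of that. This also stands. A reader might infer that the endpoint is invalid. It is not; the difficulty lies in labelling it reading activity.
- **Later visits.** A reader might infer that the four-book gap lasts to 24 months. The text gives neither the number of later books, nor the books already at home, nor losses, so persistence is possible but not shown.
- **The percentages are generic.** They show how the rejection rate grows with a shift, not that this score shifts. That is correct.
- **The Aim 3 link is inferred.** Section 5)c names no mediator score, and the frequency items would fit its wording. True, but StimQ is the only quantitative reading measure named, so the choice needs to be written down.
- **Replacing the endpoint would be costly.** Making an item subset the secondary endpoint would give up the properties reported for StimQ. This is a fair objection, and it is why the existing score should be kept.

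**Conclusion.** The overlap between what the ELP arm is given and what StimQ asks about is explicit, and nothing in the plan separates the two. The StimQ score can rise in the ELP arm, chiefly at 6 months, without any change in reading frequency. A difference would be a valid difference in home cognitive stimulation, but it would not by itself show that parents read more. The score is also a poor mediator for an aim about the intensity of reading behaviour.

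The size is unknown. The rejection rates of roughly 8% to 68% rest on assumed shifts of 0.1 to 0.5 SD, 48 per arm and no change in reading; they are not estimates for this trial. The primary PLS comparison is not touched. This is a worthwhile, inexpensive improvement to one secondary endpoint and one exploratory aim. It is not a flaw in the trial's main result.

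**What to change.** In section 5)b, keep StimQ as the secondary endpoint and state whether the total or the Read subscale is analysed.

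In section 5)c:
- prespecify a companion between-group analysis of the reading-frequency items alone;
- report the number and variety of books separately, described as partly reflecting delivery of the intervention;
- name the reading-frequency items as the Aim 3 mediator;
- state that any conclusion that parents read more will rest on the frequency items.

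The items are already collected, so the change is to wording only. Making it before analysis also avoids choosing a StimQ version after seeing results. There are two costs. The reported alpha (0.89), test-retest reliability (0.84) and Bayley correlation (0.52) are for StimQ and do not carry over to the subset. The frequency items are also still parent-reported, in an arm that receives weekly reading messages, so they narrow the ambiguity without removing reporting bias.

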Children in both study arms will be followed every 6 months until age 2. Parents will complete study measures consisting of demographic characteristics, postpartum depression symptoms, health literacy, and adverse childhood experiences at enrollment, and parents and children will complete measures of reading activity (Stim-Q), and child expressive and receptive language development (Preschool Language Scale-V) at 6, and 24 months of age. At 12, 18, and 24 months, measures of parental stress (PSI-Short Form, Appendix 9), parental depression (PHQ-9, Appendix 10) will be collected. Child social and emotional competencies will be collected at 18

and 24 months of age (ITSEA, Appendix 11). Information on reading activities and expressive and receptive language outcomes will be collected in concert with scheduled well child visits. Differences in reading activities, parental mental health, child's social/emotional competencies, and language outcomes will be assessed between groups using intention-to-treat analysis. The EHR will be reviewed for children in both arms to count the number of well child visits and examine their vaccination history.

Parents of children who are participating in the study will be informed of the results of their PLS testing in writing. Those whose children score less than 1.5 standard deviations below the mean will be informed that their children's language development is within the average range. Parents whose children who score 1.5 standard deviations or greater below the mean will be informed that their child is exhibiting delays in language development and will be referred for additional evaluations and/or services. In addition, the child's clinician will be informed of their result.

Responses to the question on the PHQ-9 will be checked to determine whether the caregiver has endorsed suicidal ideation. If they have endorsed any of the suicide questions, research staff will administer additional follow up questions and call the study licensed psychiatrist to determine course of action (see Appendix 13-Suicide Protocol). This procedure has been implemented successfully in other studies of parental depression. During the study visits, if a participant was to endorse suicidal ideations, the Appendix 13: 'Suicide Protocol' will be followed to maximize the safety of the participant. At any time, caregivers who endorse suicidal ideations will require immediate follow up with the licensed psychiatrist on call.

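### StimQ is a declared secondary endpoint at 6, 12, 18 and 24 months, but a between-group analysis is specified only at 6 and 24 months

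*Combined protocol and SAP*

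**What the plan says.** The endpoint is stated twice, consistently. The Abstract has "StimQ score differences at 6,12,18, and 24 months of age will be a secondary outcome", and section 5b (Secondary Endpoints) has "Secondary endpoints will be the difference in StimQ scores at 6, 12, 18, and 24 months of age".

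On collection, Study Procedures part c (follow-up visits at 6, 12, 18 and 24 months) states "Parents will complete measures of reading activity (Stim-Q) at each study visit". Section 3.1.2 instead gives "measures of reading activity (Stim-Q), and child expressive and receptive language development (Preschool Language Scale-V) at 6, and 24 months of age".

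On analysis, section 5c assigns t-tests to "Cross-sectional differences in StimQ scores and PLS scores between intervention and control groups at the 6 and 24 month study visits", and to ITSEA at 18 and 24 months. It then plans "regression models using longitudinal data methods that adjust for correlation in PLS scores over time", and separate regressions for the socio-emotional scores. No regression or longitudinal model is given for StimQ as an outcome in its own right.

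Two other statements touch on reading activity. Sections 3.1 and 3.1.2 make a general commitment: "Differences in reading activities, parental mental health, child's social/emotional competencies, and language outcomes will be assessed between groups using intention-to-treat analysis". The mediation analysis in section 5c includes a model for "parent-child reading activity on group assignment". Neither names a visit.

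**The concern.** A reader who tries to produce the secondary endpoint from section 5c can do so at 6 and 24 months and finds no instruction for 12 and 18. Three things follow.

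- With no test, model or key contrast named for those visits, the analyst can decide after seeing the data whether to test them, how, and which visit to emphasise.
- A t-test at 24 months uses only families who attend then. The plan expects 20% loss over two years. A family seen at 12 or 18 months but not at 24 contributes nothing to that comparison.
- Specific Aim 3 treats reading intensity as the mediator. The 12- and 18-month scores lie between the two PLS assessments, and the plan does not say whether they are used.

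The conflict in section 3.1.2 makes this worse, because a team following that section would not collect the 12- and 18-month scores at all.

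**Working it through.** **Step 1. Set the visits side by side** for the three instruments named in sections 5a and 5b.

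| Instrument | Endpoint visits | Collected | Test named in 5c | Further model in 5c |
|---|---|---|---|---|
| PLS | 6, 24 | 6, 24 | t-tests at 6, 24 | longitudinal regression |
| ITSEA | 18, 24 | 18, 24 | t-tests at 18, 24 | adjusted regression |
| StimQ | 6, 12, 18, 24 | every visit (Procedures, part c); 6, 24 (3.1.2) | t-tests at 6, 24 | none as outcome |

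StimQ is the only one of the three whose endpoint visits and named tests differ.

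**Step 2. Size of the precision question.** The plan gives no StimQ effect size, SD or power, so there is no StimQ figure to reproduce. The total of 120 children rests on PLS.

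Inputs from section 5c: 60 per arm and 20% loss, so 60 × 0.80 = 48 per arm at 24 months.

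Assumptions: loss is even and monotone, so 57, 54, 51 and 48 per arm are seen at 6, 12, 18 and 24 months; SD is equal across visits (results are in SD units); covariance is treated as known. No between-visit correlation ρ is stated. The only within-person figure is the test-retest value of 0.84 in the StimQ description, used here as the top of an assumed range from 0.3.

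- The t-test SE at 24 months is √(2/48) = 0.204.
- In a model with free group-by-visit means, the 24-month variance is 2 × [(1 − R₃)/48 + (R₃ − R₂)/51 + (R₂ − R₁)/54 + R₁/57]. Here Rₖ is the squared multiple correlation of the 24-month score with the first k visits. Under exchangeable correlation, Rₖ = kρ²/(1 + (k − 1)ρ).
- Example, ρ = 0.5: R₁ = 0.250, R₂ = 0.333, R₃ = 0.375. The bracket is 0.01302 + 0.00082 + 0.00154 + 0.00439 = 0.01977, so SE = √0.03953 = 0.199.

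| ρ (exchangeable) | t-test SE | Four-visit model SE | Reduction |
|---|---|---|---|
| 0.3 | 0.204 | 0.202 | 1.1% |
| 0.5 | 0.204 | 0.199 | 2.6% |
| 0.7 | 0.204 | 0.195 | 4.6% |
| 0.84 | 0.204 | 0.192 | 6.2% |

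Under AR(1), with R₁ = ρ⁶, R₂ = ρ⁴ and R₃ = ρ², the reduction runs from 0.3% (ρ = 0.3) to 4.3% (ρ = 0.84). The 6-month SE is √(2/57) = 0.187 either way. With complete data every denominator is equal, the R terms cancel, and the gain is zero.

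**Step 3. Why simply adding two t-tests is not a clean repair.** With independent tests at 0.05, the chance of at least one false positive is 1 − 0.95² = 9.8% for two visits and 1 − 0.95⁴ = 18.5% for four. Repeated scores from one family are positively correlated, so the true figures would be lower, but a named key contrast is still needed.

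**The case against.** The strongest reply is that the plan does not say the 12- and 18-month data go unused. Section 5c opens with summary statistics and an intention-to-treat comparison, sections 3.1 and 3.1.2 promise a comparison of reading activities without limiting the visits, and the mediation analysis could draw on any visit. This stands against a claim that the data are discarded. It does not close the gap, because none of these statements fixes a visit, a model or a contrast.

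A reader might also infer that precision is being thrown away and that using all four visits is worth 10% to 37% more families. The documents do not support that. The figures come from comparing a four-visit average with a 6-and-24-month average. With exchangeable correlation, the variance of a k-visit mean is (1 + (k − 1)ρ)/k, so the ratio of two visits to four is 0.65/0.475 = 1.37 at ρ = 0.3, 0.75/0.625 = 1.20 at 0.5 and 0.85/0.775 = 1.10 at 0.7. The plan defines neither average. Under AR(1) the four-visit average has about 8% less variance than the two-visit one at ρ = 0.5, but about 1% more at 0.7 and 2% more at 0.84. The contrasts the plan does name gain only what Step 2 shows.

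Nor do the documents require the average as the single test. The arms receive different literacy promotion only until 6 months, so 6 months (end of the contrast) and 24 months (persistence) are distinct questions, and an average would blend them if an effect fades. Averaging also needs StimQ scores comparable across ages, which the documents do not establish.

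Finally, the endpoint could be cut to 6 and 24 months, with 12 and 18 labelled descriptive. That would remove the mismatch, but it narrows an endpoint stated in two places and leaves the 24-month comparison restricted to attendees.

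**Conclusion.** The point holds as a mismatch between endpoint and analysis. Two of the four declared StimQ visits have no specified between-group analysis, and section 3.1.2 contradicts the Abstract, Study Procedures part c and section 5b on which visits apply. This part rests on the text alone.

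The consequences are room for post hoc choice of visit or model and a 24-month comparison limited to attendees. In the assumed dropout pattern, 57 − 48 = 9 families per arm have a StimQ score but none at 24 months; 54 − 48 = 6 of them have a 12- or 18-month score. Precision is a minor matter: about 1% to 6% of the 24-month SE under exchangeable correlation of 0.3 to 0.84 with 20% monotone dropout, less under AR(1), and none with complete data.

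This is a secondary endpoint; the primary endpoint and the sample size are unaffected. The change is worth making because it costs almost nothing.

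**What to change.** 1. Reconcile the StimQ schedule in section 3.1.2 with the Abstract, Study Procedures part c and section 5b.
2. In section 5c, replace the StimQ t-tests with one repeated-measures mixed model using all four visits and every randomised family with at least one StimQ score. Include group, visit and group-by-visit, an unstructured covariance, and the demographic covariates used for the PLS model. Section 5c does not list those covariates, so name them.
3. Report all four visit-specific differences with confidence intervals, and name the key contrast before the data are seen. Whether that is one visit or the four-visit average is for the sponsor to decide.
4. State which StimQ visits enter the mediation analysis.

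The cost is a few lines of text and slightly more analysis in Stata, which is already named; no new data are needed if StimQ is collected at each visit. The trade-off is a modelling assumption: families who miss the 24-month visit contribute under missing-at-random, which should be stated. Families with no StimQ score at all still contribute nothing.
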